## Study protocol

At the beginning of the intervention, an initial evaluation was carried out using the different tests for all the participants (baseline). During the intervention, the users received weekly sessions (individual and group) via videoconference from a social worker, a psychologist, a sociocultural activities technician, and a physiotherapist. Appointments were previously arranged according to the availability of each user. Participants were classified according to the following therapeutic profiles: active aging, emotional disorders, unwanted loneliness, residential care center users, cognitive impairment, physical limitations and social exclusion. Table 1 shows a typical schedule for one of the participants. Nevertheless, the number of sessions may vary depending on the therapeutic profile of the participants. For example, the unwanted loneliness and social exclusion profiles have 5 weekly sessions, the physical or cognitive limitation profiles have 3 to 3.5 weekly sessions, while the active aging profile has 2 to 2.5 weekly sessions. Individual sessions were held on a fortnightly basis.

Table 1. Schedule of a typical weekly intervention for one of the participants.

Time	Monday	Tuesday	Wednesday	Thursday	Friday
12:00-13:00	Recreational group session		Cognitive group session with psychologist		Individual follow-up session with social worker/ psychologist
17:00-18:00				Gym group session with physiotherapist	

Approximately halfway through the intervention, the same instruments were applied again and right at the end of the intervention, in order to verify our hypothesis. Therefore, in addition to the baseline measures, we obtained two more measures (an intermediate data collection at the middle of the intervention and another one at the end).

The following inventories were used as instruments to measure the effectiveness of the intervention. To cognitively assess the participants, the MMSE (Folstein et al., 1975) was used. The FUMAT scale (Gómez et al., 2008) was used to assess quality of life by means of 8 different dimensions. The abbreviated version of the Yesavage Geriatric Depression Scale (Martínez de la Iglesia et al., 2002) was used to assess depression. Loneliness was assessed using the revised ESTE scale (ESTE-R) (Rubio & Aleixandre, 1999). The Barthel's scale (F.I. Mahoney & Barthel, 1965) was used to measure the subjects' functional capacity to perform basic activities and tasks of daily living (ADL) whereas the Lawton and Brody's test (Lawton & Brody, 1970) was used to measure the ability to perform instrumental activities of daily living (IADL). Finally, Tinetti's scale (Tinetti, 1986) was used to assess the balance and gait of older adults and determine the risk of falls.

## Statistical analysis plan

Initially, the Kolmogorov-Smirnov test was applied to assess the normality of the variables. Only the Fumat test values showed a normal distribution, so parametric statistics were used for the analysis of this particular case. The remaining variables showed a non-normal distribution, so nonparametric tests were used. Data were reported as mean  $\pm$  SD. The demographic and clinical variables of the groups at baseline were compared using the chi-square test for categorical variables and the independent-samples t test for quantitative data.

This research also performed Wilcoxon signed rank tests to examine whether there was a statistically significant difference in a group of participants between time intervals (t0: baseline, t1:mid intervention, t2: end of intervention). In addition, a 2-way repeated measure analysis of Variance (ANOVA) was performed to study the interaction effects of time (at baseline, mid intervention and end of intervention) in the two intervention groups (experimental and control) in the Fumat scale, together with the plot of the estimated marginal means. Partial eta-squared ( $\eta_p^2$ ) was used to categorize effect sizes when the distribution was normal. In this case,  $\eta_p^2 = 0.01$  for a small effect, 0.06 for a medium effect, and 0.14 for a large effect, respectively. When the data did not follow a normal distribution, Cohen's r ratio ( $r = Z/\sqrt{N}$ ) was used. This ratio indicates that a large effect corresponds to  $r = 0.50$ , a medium effect to  $r = 0.30$ , and a small effect to  $r = 0.10$ , respectively. The size of the effect will indicate us the practical relevance. Version 26 SPSS software was used to perform all the statistical analyses. The level of significance was set at 0.05.

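### The baseline t tests depart from the plan's own nonparametric rule, cannot show that the arms are alike under any choice of test, and no baseline covariate enters the only between-arm analysis

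*Combined protocol and SAP*

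**What the plan says.** All of the relevant text is in the Statistical analysis plan section.

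- **Distribution rule.** After a Kolmogorov-Smirnov test: "Only the Fumat test values showed a normal distribution, so parametric statistics were used for the analysis of this particular case". Then: "The remaining variables showed a non-normal distribution, so nonparametric tests were used".
- **Summary statistic.** "Data were reported as mean" and SD, with no exception for the non-normal variables.
- **Baseline comparison.** "The demographic and clinical variables of the groups at baseline were compared", with the method given as "compared using the chi-square test for categorical variables and the independent-samples t test for quantitative data". No exception is made here either.
- **Later analyses.** Wilcoxon signed rank tests are used to "examine whether there was a statistically significant difference in a group of participants between time intervals", which is a within-group question. For FUMAT, "a 2-way repeated measure analysis of Variance (ANOVA) was performed to study the interaction effects of time" in the experimental and control groups. No covariate is named in either analysis.
- **Significance level.** "The level of significance was set at 0.05"; sidedness is not given.

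The Study protocol section says that all participants were assessed with the instruments at baseline. It lists MMSE, FUMAT, the abbreviated Yesavage scale, ESTE-R, Barthel, Lawton-Brody and Tinetti. It also describes seven therapeutic profiles, ranging from active aging to cognitive impairment and residential care. The documents give no sample size, allocation ratio, method of assignment or SD.

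**The concern.** Two separate matters meet in the baseline clause.

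The first is consistency. Six of the seven scales fall under the nonparametric rule, yet the baseline clause sends all quantitative data to a t test. The clause does not name the scales, but they are the only clinical measures the documents describe, so the natural reading includes them.

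The second carries more weight. The baseline comparison is the only check on the likeness of the arms that the documents describe, and no method of assignment is stated. A p-value above 0.05 in a study of modest size says little about whether the arms are alike. Nothing in the analysis depends on the comparison in any case: no baseline variable enters a later model, whether the test is significant or not. In a population this mixed, the arms could differ in age, cognition or function, and any of these may predict how quality of life changes. Such a difference would pass into the FUMAT group-by-time result.

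**Working it through.** The plan states no sample size, power or baseline SD, so it has no figure to reproduce. The check takes three steps.

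**1. How often would a baseline test notice a real gap?**

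Input from the plan: significance level 0.05. Assumed: two-sided test, equal arms, n = 25, 40 or 60 per arm, true gap d = 0.3 SD, normal data.

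- Noncentrality: d × √(n/2).
- Degrees of freedom: 2n − 2.
- Power: the probability that a noncentral t exceeds the critical value t(0.975, 2n − 2) in absolute value.
- Largest observed gap that is still non-significant: t(0.975, 2n − 2) × √(2/n), in SD units.

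| n per arm | Critical t (df) | Noncentrality | Power at 0.3 SD | Largest non-significant gap |
|---|---|---|---|---|
| 25 | 2.011 (48) | 0.3 × √12.5 = 1.061 | 0.180 | 2.011 × 0.283 = 0.57 SD |
| 40 | 1.991 (78) | 0.3 × √20 = 1.342 | 0.263 | 1.991 × 0.224 = 0.45 SD |
| 60 | 1.980 (118) | 0.3 × √30 = 1.643 | 0.371 | 1.980 × 0.183 = 0.36 SD |

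So a 0.3 SD gap is missed 63% to 82% of the time. These are normal-theory figures. They show the limit of significance testing at these sizes, not a penalty for using a t test on skewed data.

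**2. Does the choice of test drive the misses?**

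Simulations used invented scale shapes, since the documents give none.

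- *Equal arms.* On three skewed, bounded scales with 20 to 100 per arm, the t test rejected 4.1% to 5.5% of the time and Mann-Whitney 3.8% to 5.8%. Both hold their level.
- *Location shift of 0.5 SD, 30 per arm.* The t test detected it about 50% of the time, nearly the same as on normal data (49%). Mann-Whitney detected it 65% to 84% of the time.
- *Longer tail with the same 0.5 SD mean difference, 30 per arm.* The order reverses: t test 28% to 41%, Mann-Whitney 22% to 35%.
- *Ceiling scale, 40 per arm.* The score is 100 with probability p, otherwise 100 minus 5 times a geometric variable with parameter q, truncated at 0. With p = 0.6 versus 0.3 (q = 0.12 in both arms), detection is about 0.43 for t and 0.70 for Mann-Whitney. With p = 0.6 in both arms and q = 0.20 versus 0.07, it is about 0.47 for t and 0.10 for Mann-Whitney.

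Which test is more sensitive therefore depends on where the arms differ.

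**3. What does the between-arm analysis leave in?**

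Let δ be the between-arm gap in a baseline variable X, and β the effect of X on change in FUMAT.

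- If the only imbalance is a constant offset in FUMAT, it is present at every visit and cancels from the group-by-time term.
- If X predicts change, the group-by-time term contains β × δ in addition to any intervention effect.
- Adding X only as a main effect would not remove this, because a fixed baseline variable then shifts all visits equally. X must also interact with time.

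For the six other scales the plan describes only within-group tests, so there is no between-arm model for a covariate to enter.

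**The case against.** The strongest reply is that this is a wording slip with no consequence: the baseline test feeds no later analysis, so changing it alters no efficacy result. That stands for the choice of test. It does not answer the absence of covariates, which would remain if the test were changed.

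A reader might infer that using a t test on non-normal scales is what makes imbalance likely to be missed. The working does not support that. The t test kept its nominal level on skewed data, and its power at a 0.5 SD shift was about the same as for normal data. The rank test did worse when only the impaired tail differed, and that is plausible in a study enrolling both active-aging and impaired participants. For the same reason mean and SD should stay in the table, because medians alone could hide a difference in severe impairment.

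A reader might also infer that the plan treats p > 0.05 as proof of comparability, or adjusts only when the test is significant. It states neither; it says only that the groups were compared.

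Finally, FUMAT is the one scale for which the t test does fit the plan's rule, and its group-by-time term already removes a constant FUMAT offset. Both points are right. What remains is imbalance in other predictors of change.

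**Conclusion.** The point holds in three limited parts.

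1. The baseline t test for all quantitative data contradicts the plan's nonparametric rule for the variables other than FUMAT. This is a matter of consistency and has no effect on the efficacy results.
2. No baseline significance test can show that the arms are alike. At an assumed 25 to 60 per arm, a 0.3 SD gap is detected only 18% to 37% of the time, and observed gaps of up to 0.57 to 0.36 SD would be non-significant.
3. The only between-arm analysis has no baseline covariate, so imbalance in predictors of FUMAT change other than a constant FUMAT offset stays in the result.

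The third part is the reason to act. Its size cannot be given, because the documents report neither the arms' baseline values nor how strongly those values predict change. The figures in the second part rest on assumed arm sizes, equal allocation, a two-sided test and normal data. The comparison of the two tests rests on invented scale shapes and supports only the statement that neither is generally more sensitive. The absence of any between-arm test for the six other scales is a larger, separate gap.

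**What to change.** - **Between-arm model.** Name a small set of already collected prognostic baseline variables, for example age and sex (if collected), baseline cognition (MMSE) and baseline function (Barthel or Lawton-Brody). Enter them in the FUMAT group-by-time model together with their interactions with time, regardless of any baseline test. Choose them because they are expected to predict outcome, not because of an observed imbalance. The plan already reports distributional findings, so state openly when the set was chosen.
- **Baseline table.** Give a standardised between-arm difference for each variable. Show median (IQR) alongside mean and SD for the six non-normal scales. State that baseline p-values are not used to judge comparability.
- **If baseline tests are kept.** Use a rank test such as Mann-Whitney for the variables the plan calls non-normal, so that the paragraph agrees with itself. Do not claim that it is generally more sensitive.

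The cost is a few degrees of freedom in one model, a reformatted baseline table and some SAP wording. No new data are needed, provided the chosen covariates were collected.

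### On six of the seven effectiveness scales the plan specifies no post-baseline comparison of experimental with control; the only named test of change, and the only named source of its effect size, is within-group

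*Combined protocol and SAP*

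**What the plan says.** The Study protocol section introduces seven scales (MMSE, FUMAT, abbreviated Yesavage, ESTE-R, Barthel, Lawton-Brody, Tinetti) with the sentence "The following inventories were used as instruments to measure the effectiveness of the intervention". It does not rank them. At the start, "an initial evaluation was carried out using the different tests for all the participants (baseline"). Later, "the same instruments were applied again and right at the end of the intervention, in order to verify our hypothesis".

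The Statistical analysis plan section treats FUMAT as normally distributed. For the other scales it says: "The remaining variables showed a non-normal distribution, so nonparametric tests were used". Besides the normality check it names four procedures:

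- the chi-square test and the independent-samples t test, both for comparing the groups at baseline;
- the Wilcoxon signed-rank test, "to examine whether there was a statistically significant difference in a group of participants between time intervals" (t0, t1, t2);
- a two-way repeated-measures ANOVA for the time-by-group interaction, "in the two intervention groups (experimental and control) in the Fumat scale".

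On effect size the section says "The size of the effect will indicate us the practical relevance". The measure that applies "When the data did not follow a normal distribution" is r = Z/√N, with 0.10, 0.30 and 0.50 as small, medium and large. The test that supplies Z is not stated.

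**The concern.** The trial has a control group, but on six scales the specified analysis of change does not use it. A paired test within one group shows whether scores moved. It cannot show why. Repeating the same instruments, natural change over the period and regression to the mean all move scores without any intervention effect, and they are added to any effect there is. The direction of the distortion is unknown. A shared improvement would look like benefit, and a shared decline, which is possible in older adults with cognitive or physical limitations, could cancel a real benefit.

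The effect size inherits the problem. The plan uses it to judge whether a result matters in practice. If Z comes from the Wilcoxon test, r measures the size of within-group change and not the size of the intervention effect.

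**Working it through.** **1. Match scales to tests.** The documents give no sample size or power figure, so there is no stated number to reproduce. The check is a count.

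| Scales | Named test of change over time | Named post-baseline test of experimental against control |
|---|---|---|
| FUMAT (1) | time-by-group ANOVA | the same ANOVA |
| MMSE, Yesavage, ESTE-R, Barthel, Lawton-Brody, Tinetti (7 - 1 = 6) | Wilcoxon signed-rank | none |

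The chi-square and t tests do compare the groups, but only at baseline. For change on the six scales, the Wilcoxon test is the only named procedure that yields a Z.

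**2. What r measures when the intervention does nothing.** Assume a normal change score with the same shift of d SDs in both arms. In large samples the signed-rank statistic gives Z ≈ √(3n)·[Φ(√2·d) - 0.5], with n pairs. Hence r = Z/√n tends to √3·[Φ(√2·d) - 0.5], whatever the sample size.

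- d = 0.2: r = 0.193
- d = 0.3: r = 0.285
- d = 0.4: r = 0.371

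If N counts observations rather than pairs, divide by √2: 0.136, 0.201, 0.262. On the plan's labels these values run from small to medium, while the between-arm effect is 0. In simulations at d = 0.3 with an assumed 30 to 100 per arm (N = pairs), mean r was 0.28, and r reached 0.30 in 43-47% of runs.

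**3. The other direction.** With d = -0.3 in both arms, r is about -0.28 and the between-arm effect is again 0. If the intervention also gave a true gain of 0.3 SD, the experimental arm's change would be -0.3 + 0.3 = 0. Its r would tend to 0, although the arms differ by 0.3 SD.

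**4. Separate tests in each arm do not fill the gap.** With equal true change and within-arm power p, the chance of a significant result in the experimental arm only is p(1 - p), at most 0.5 × 0.5 = 25%. Simulation (assumed 20, 40 or 80 per arm; shift 0.3 or 0.5 SD; 3,000 replicates) gave 0.8% to 24.5%. A Mann-Whitney test of change between arms gave 3.9% to 5.2%.

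**5. Which between-arm comparison.** The documents do not say how the arms were formed. The table gives false rejection rates with no intervention effect (assumed true-score SD 1, error SD 0.6, common change 0.3 change-SD, 30 to 100 per arm, two-sided 0.05). Where two ranges appear, they are normal scores / an assumed 0-30 ceiling scale.

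| Arms | Mann-Whitney on change | ANCOVA on ranks | Proportional odds (ceiling only) |
|---|---|---|---|
| Comparable | 4-5% / 5-6% | 4-5% / 5-6% | 6% |
| Experimental arm drawn from low observed baselines | 20-53% / 30-75% | 6-7% / 7-8% | 7-8% |
| Stable 0.5 SD true difference | 5% / 4-5% | 11-22% / 10-23% | 10-24% |

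With comparable arms all three hold close to 5%. With imbalance, change scores fail in one case and baseline adjustment in the other.

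**6. Multiplicity.** Six independent tests at 0.05 give 1 - 0.95^6 = 0.265 for at least one false positive, or about 0.21 at an assumed correlation of 0.5.

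**The case against.** The strongest reply is that the analysis section is a short summary in the past tense. It refers to nonparametric tests in general and only then describes the Wilcoxon tests as something further, so an unnamed between-group test such as Mann-Whitney may have been run and may have supplied Z. This cannot be excluded. It does not close the gap: the section names its other tests, ties its post-baseline group comparison to FUMAT, and gives no test, time point or contrast for the other six scales.

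A reader might therefore infer that the investigators did judge effectiveness from within-group change, or that reported findings are wrong. The documents do not support either inference. They report no Wilcoxon result and state no effectiveness conclusion.

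Two further points have some weight. Neither the hypothesis nor a primary outcome is stated; if FUMAT were primary, the gap would concern secondary scales. However, all seven scales are presented equally as effectiveness measures. Also, the size of any distortion in this trial is unknown, because the shifts, SDs and sample sizes above are assumed.

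**Conclusion.** The point holds as a gap in the specified analysis. Followed as written, the plan leaves the control group unused after baseline on six of seven scales, and neither the Wilcoxon test nor an r derived from it can answer the effectiveness question there. That conclusion rests on the text alone and is firm. It is more than a missing detail, and it should be resolved before any effectiveness statement is made on these scales.

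The figure of about 0.28 (or -0.28) at a shared shift of 0.3 SD assumes normal change scores and N counted as pairs. It shows the mechanism and does not estimate this trial's error. It would be tempting to conclude that the plan overstates benefit, but the direction depends on whether the arms improved or declined, which the documents do not say. Nor do they support one replacement method as best in all circumstances, because allocation is not described.

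**What to change.** For each of the six scales, base any effectiveness conclusion on an experimental-versus-control comparison of the t0-to-t2 outcome, with an effect estimate and 95% CI. Treat the Wilcoxon tests and their r as descriptive.

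- **State how the arms were allocated.** If at random, use a baseline-adjusted model: proportional odds or rank-based ANCOVA of the t2 score on arm and t0 score. If not, report both the baseline-adjusted comparison and the between-arm comparison of change, since each can mislead under a different kind of imbalance, and limit causal wording.
- **If a between-group test was already run, name and report it.** Label any newly added test post hoc, because the section already reports normality results.
- **Report all six results** and say whether they are adjusted for multiplicity.
- **Confirm that controls have follow-up scores on these scales.** Where they do not, draw no effectiveness conclusion.

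The cost is SAP wording and a few more analyses of data that appear to have been collected. A multiplicity adjustment would lower power per scale. Any significant within-group result would no longer support an effectiveness claim by itself.

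### The FUMAT repeated-measures ANOVA cannot use a participant with a missed follow-up visit and, uncorrected, relies on sphericity; the plan addresses neither

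*Combined protocol and SAP*

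**What the plan says.** The Statistical analysis plan defines three occasions ("t0: baseline, t1:mid intervention, t2: end of intervention") and states that "a 2-way repeated measure analysis of Variance (ANOVA) was performed to study the interaction effects of time" "in the two intervention groups (experimental and control) in the Fumat scale". Partial eta-squared is the effect size planned for normally distributed data, and a plot of estimated marginal means accompanies the ANOVA. The Wilcoxon signed-rank tests look at change over time within a group, so the ANOVA interaction is the only named contrast of the two groups on an outcome.

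The ANOVA was chosen after a Kolmogorov-Smirnov check: "Only the Fumat test values showed a normal distribution, so parametric statistics were used". No other assumption check is described. On software and error rate the plan says "Version 26 SPSS software was used to perform all the statistical analyses" and "The level of significance was set at 0.05". It does not name the procedure, or say whether the uncorrected, epsilon-corrected or multivariate test is read.

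The Study protocol says that all participants were assessed at baseline and that "in addition to the baseline measures, we obtained two more measures". It does not say how many people gave the second and third measures. There is no missing-data rule, imputation method, analysis population or count per visit.

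**The concern.** There are two separate issues.

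**Missed visits.** A classical repeated-measures ANOVA works on complete triplets. A participant with t0 and t1 but no t2 contributes nothing, although two of the three values were observed. The therapeutic profiles in the Study protocol include cognitive impairment, physical limitations and residential care. In such people a missed assessment may well follow decline, so those who remain would look better than the whole group. A missing-data sentence alone would not cure this, because the method cannot use a partial record.

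**Sphericity.** With three occasions, the uncorrected group-by-time F test holds its level only if the variances of all pairwise differences are equal. That fails if, for example, mid and end values correlate more closely with each other than with baseline. A normality test says nothing about it.

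At stake are the precision and possible bias of the one between-group outcome result, and the meaning of its p-value.

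**Working it through.** **Inputs from the documents:** 2 groups, 3 occasions, significance level 0.05. **Not given, so assumed:** group sizes, attrition, visit correlations.

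**1. The plan's own figure.** Simulating the group-by-time F test with no effect, under sphericity and with equal covariance in both groups, gives rejection in 5.0–5.1% of runs (15+15, 50+50 and 100+50 participants). The 0.05 level is reproduced when the assumption holds.

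**2. Participants lost.** Let m be the proportion missing a follow-up visit. If only t2 is missed, the loss is m. If t1 and t2 are missed independently, the loss is 1 − (1 − m)².

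| m | only t2 missed | independent misses |
|---|---|---|
| 5% | 5% | 1 − 0.95² = 9.8% |
| 10% | 10% | 1 − 0.90² = 19% |
| 15% | 15% | 1 − 0.85² = 27.8% |
| 20% | 20% | 1 − 0.80² = 36% |

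**3. Bias within one arm.** Assume SD 1 at each visit, true change 0, and dropout before t2 with a log-odds that rises by 1 for each outcome SD of decline from t0 to t1. The table gives completers' mean t0–t2 change in SD.

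| Dropout | correlation 0.7 for every pair | AR(1) 0.7 (t0–t2 correlation 0.49) |
|---|---|---|
| 10% | 0.03 | 0.05 |
| 20% | 0.06 | 0.09 |
| 30% | 0.08 | 0.14 |

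Completers' t0–t1 change is larger (0.06, 0.11, 0.16), but the end-of-intervention figure is the relevant one. The scale of the slope matters somewhat. A log-odds of 1 per SD of the change, which is √(2 × 0.3) = 0.77 outcome SD, gives 0.04–0.10 and 0.06–0.17 instead.

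Predicting t2 from t0 and t1 for everyone, which is the likelihood estimate for this pattern, gives 0.00. That follows from the set-up, because dropout depends only on observed values. It shows what such an analysis does when missing-at-random holds, not that it holds here.

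**4. Bias in the arm contrast** = bias in the experimental arm − bias in the control arm. With the same dropout mechanism and rate in both arms it is 0. With 30% against 10% under AR(1) it is 0.14 − 0.05 = 0.09 SD.

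**5. Error rate of the uncorrected F test.** For three occasions epsilon lies between 1/(3 − 1) = 0.5 and 1. With large samples:

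| epsilon | 1.0 | 0.9 | 0.8 | 0.7 | 0.6 | 0.5 |
|---|---|---|---|---|---|---|
| type I error | 5.0% | 5.4% | 5.9% | 6.6% | 7.4% | 8.3% |

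The floor is analytic: P[F(1, N−2) > F₀.₉₅(2, 2(N−2))] is 8.6% for N = 30 and 8.4% for N = 100.

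Simulated with 40 per arm (correlations in the order t0–t1, t0–t2, t1–t2):

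| Correlations | epsilon | type I error |
|---|---|---|
| 0.7, 0.49, 0.7 (AR(1) 0.7) | 0.87 | 5.5% |
| 0.8, 0.64, 0.8 (AR(1) 0.8) | 0.85 | 5.6% |
| 0.7, 0.7, 0.85 | 0.86 | 5.8% |
| 0.6, 0.6, 0.85 | 0.78 | 6.2% |
| 0.5, 0.5, 0.9 | 0.65 | about 7% |

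With the Greenhouse-Geisser correction the rate is 4.5–5.1% in every scenario run.

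**The case against.** The documents report no missed visit, dropout or exclusion. If everyone attended all three assessments, nothing was deleted. Nor do they say which F test was read, and silence about a correction is not evidence that none was used; a corrected or multivariate test holds its level. A reader might therefore infer that the FUMAT result is a completers-only result with an error rate above 5%, and the documents do not support that. The first half needs missed visits without imputation. The second needs both departure from sphericity and use of the uncorrected test.

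A reader might also join the two issues, as if deletion caused the inflation. It does not, unless missingness depends on outcome differently by group. Nor does losing decliners always overstate change: if the true course is decline, it understates it.

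A further tempting step is to say that the Wilcoxon tests compare different people at each pair of visits. The plan does not say how missing pairs were treated, so that is not claimed here.

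It can also be said that replacing the model goes further than the gap requires, since a corrected p-value settles the sphericity issue. That is right for sphericity. It does nothing for participants with partial records, where the limit lies in the method itself.

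**Conclusion.** The point holds in conditional form. The named method cannot use a participant with a missed follow-up visit unless values are imputed, and no imputation is planned. Its uncorrected test relies on a condition that the plan neither checks nor corrects for. Missed visits are the weightier issue:

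- **Loss of participants:** 5–20% or 10–36% for miss rates of 5–20%, depending on the pattern.
- **Bias in an affected arm at end of intervention:** about 0.03–0.08 SD with equal correlations of 0.7, or 0.05–0.14 SD under AR(1) 0.7. This assumes 10–30% dropout after decline and no true change. Only the difference between arms reaches the contrast.
- **Type I error, if the uncorrected test is used:** about 5.4–7% for epsilon between 0.9 and 0.65, and at most about 8–9%. This assumes equal covariance in the two groups. Unequal covariance with unequal group sizes could move it either way, and group sizes are not given.

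If no visit was missed and a corrected test was read, neither effect arises; the plan as written does not let a reader tell.

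**What to change.** Make the FUMAT analysis a linear mixed model fitted by REML with unstructured covariance. The outcomes are FUMAT at t1 and t2; the terms are arm, visit, arm-by-visit, baseline FUMAT and baseline-by-visit. Include every participant with a baseline and at least one later visit, analysed in the assigned group. Report the arm difference at t2 with its 95% confidence interval, and the number assessed per arm and visit.

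If the ANOVA is kept as a supporting analysis, report epsilon, the Greenhouse-Geisser p-value and the number excluded per arm.

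The cost is a paragraph of SAP text and one further procedure in the software already named, with no new data. The mixed model relies on missing-at-random, which cannot be verified from the data and should be stated. If the counts show that no visit was missed, little is lost by the change.

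### FUMAT: practical relevance is read from partial eta-squared, and no between-group difference in change with a confidence interval is specified

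*Combined protocol and SAP*

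**What the plan says.** All of the following is in the section Statistical analysis plan unless noted.

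- **Comparisons with control.** For FUMAT, a "2-way repeated measure analysis of Variance (ANOVA) was performed to study the interaction effects of time (at baseline, mid intervention and end of intervention", with experimental and control as the group factor, "together with the plot of the estimated marginal means".
- **Other named tests.** "The demographic and clinical variables of the groups at baseline were compared using the chi-square test" or a t test, so these are baseline comparisons. The Wilcoxon signed rank tests ask "whether there was a statistically significant difference in a group of participants between time intervals", so they are within-group. The section also says in general terms that nonparametric methods were used for the non-normal variables, but names no between-group one.
- **Effect size.** For FUMAT, the one outcome judged normal, partial eta-squared "was used to categorize effect sizes when the distribution was normal", with cut-offs of 0.01, 0.06 and 0.14. Its role is then stated: "The size of the effect will indicate us the practical relevance".
- **Descriptive reporting.** "Data were reported as mean" with SD. Whether this is by arm and visit is not said.
- **Score analysed.** Under Study protocol, FUMAT "was used to assess quality of life by means of 8 different dimensions". The analysis section refers only to the scale, so total or dimension is not stated.

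The text mentions no confidence interval, no group difference in change, no follow-up contrast and no primary time point.

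**The concern.** With two groups and three visits, the interaction has 2 degrees of freedom. It asks whether the two profiles differ in shape. Its partial eta-squared has no sign, is tied to no visit and is not in FUMAT points, yet it is the quantity the plan uses to decide whether the result matters in practice.

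The means and the plot may let a reader see which way and when the groups diverged. They do not say how precisely the difference in change was estimated. The trial's one named controlled comparison could therefore be reported as a small, medium or large effect without an interval for how many more, or fewer, points the experimental group gained.

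**Working it through.** The documents give no sample size, SD, effect or correlation, so there is no stated figure to reproduce. Every numerical input below is assumed.

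**1. Why the effect size cannot separate the patterns.** Let d0, d1, d2 be the experimental-minus-control differences at the three visits, with mean m and n participants per arm. In a balanced design the interaction sum of squares from the means is

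A = (n/2) × [(d0 − m)² + (d1 − m)² + (d2 − m)²].

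The error term depends on the covariance of the visits and not on the d's. So, for any covariance shared by both arms, partial eta-squared depends on the pattern only through the bracket. For an effect of 0.4 SD:

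- lasting benefit (0, 0.4, 0.4): m = 0.267, bracket = 0.0711 + 0.0178 + 0.0178 = 0.1067
- benefit gone by the end (0, 0.4, 0): m = 0.133, bracket = 0.0178 + 0.0711 + 0.0178 = 0.1067
- late benefit (0, 0, 0.4): 0.1067
- harm (0, −0.4, −0.4): 0.1067

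With n = 50 (N = 100), A = 25 × 0.1067 = 2.667. With equal SDs and a common correlation rho, the population value is A/(A + N × 2(1 − rho)). That is 2.667/102.667 = 0.026 at rho 0.5 and 2.667/42.667 = 0.063 at rho 0.8, the same for all four patterns. The same difference in points thus moves from below to above the plan's 0.06 cut-off solely because of rho.

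**2. The same point in a worked data set.** Assumed: 50 per arm, within-person SD 5, between-person SD 8, group shift of 4 points. Every row has F = 5.66, p = 0.0041 and partial eta-squared 0.0546.

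| Pattern | Difference in change, t0 to t1 (95% CI) | Difference in change, t0 to t2 (95% CI) |
|---|---|---|
| Benefit at end only | 0.00 (−2.86 to 2.86) | +4.00 (1.41 to 6.59) |
| Harm at end only | 0.00 (−2.86 to 2.86) | −4.00 (−6.59 to −1.41) |
| Benefit at mid only | +4.00 (1.14 to 6.86) | 0.00 (−2.59 to 2.59) |
| Benefit at both | +4.00 (1.14 to 6.86) | +4.00 (1.41 to 6.59) |

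The two contrasts separate what the effect size merges.

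**3. What means and SDs leave open.** If given by arm and visit, they allow a crude interval for the difference at a single visit. For the difference in change, with equal SDs,

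SE = SD × sqrt[(2 − 2rho) × 2/n],

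and rho is not recoverable from the means and SDs. With n = 50 and t = 1.984 on 98 df:

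- rho 0.5: 1.984 × sqrt(1.0 × 0.04) = 0.40 SD
- rho 0.8: 1.984 × sqrt(0.4 × 0.04) = 0.25 SD

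An observed difference in change of 0.30 SD then has a 95% CI of 0.30 ± 0.40 = −0.10 to 0.70, or 0.30 ± 0.25 = 0.05 to 0.55. The printed means and SDs would be identical, but one interval includes zero and the other does not. The ratio of the widths, sqrt(0.4/1.0) = 0.63, does not depend on n.

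**The case against.** The strongest reply is that the plan does not rely on partial eta-squared alone. The sentence that names the ANOVA also promises the marginal-means plot, whose purpose is to show direction and timing, and means with SDs are reported as well. That stands: a reader might infer that direction would be hidden, and the documents do not support that. What remains is that neither item is specified as a difference in change, and neither comes with an interval for one.

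A reader could try to recover the error term from F and the six cell means. The plan does not say that these will all be reported. The resulting interval would also rely on sphericity, meaning equal variances of the pairwise differences between visits.

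The text is a short summary in the past tense, and its general references to parametric and nonparametric methods could cover follow-up contrasts. This is a fair limit: the finding is that none is specified, not that none was done.

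A reader might also take the final visit as the primary time point. The sentence under Study protocol that links measurement to the hypothesis covers both the mid and the final assessment, so it does not single one out. Nor would a single contrast bring more power as a rule; it can have less than the omnibus test.

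**Conclusion.** The point holds as a gap in estimation and reporting. The ANOVA is a legitimate test of differential change and nothing here makes it invalid. The weakness is that practical relevance rests on an unsigned statistic tied to no visit, while the estimate that would answer the question, a between-group difference in FUMAT change with an interval, is not specified and cannot be rebuilt from means and SDs.

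That the patterns share one effect size is algebra. It needs only equal arm sizes, a covariance shared by both arms and effects of equal size; it does not depend on the sample size. The interval figures are illustrative: they rest on an assumed 50 per arm, equal SDs and correlations of 0.5 and 0.8. They show that the missing correlation can change the reading of a result, not that it did so in this trial.

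This should be changed, because it concerns the only named post-baseline comparison with control and the remedy is cheap.

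**What to change.** Keep the ANOVA and the plot. Judge practical relevance from the experimental-minus-control difference in FUMAT change, in points with 95% CI, and report it for both t0 to t1 and t0 to t2, since no primary time point is named. Take both contrasts from a mixed model with all three visits as outcomes, with group, time and group × time, and an unstructured covariance so that the intervals do not rely on sphericity (SPSS MIXED). If the data are complete, an independent-samples t interval on the change scores gives the same contrasts. State whether the score is the FUMAT total or a dimension.

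Cost: a little extra analysis with the same data and software. It must be labelled a post hoc re-analysis, because the plan already reports the normality results and so the data had been examined. There is no gain in power to claim; the retained omnibus test covers the cases where a single contrast has less. The benefit is a signed estimate in scale points with its uncertainty.
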